8.1.8 C-SSRS

The US FDA recommends the use of a suicidality assessment instrument that maps to the Columbia Classification Algorithm for Suicide Assessment (C-CASA)⁶². The C-CASA was developed to assist the FDA in coding suicidality data accumulated during the conduct of clinical trials of antidepressant drugs. One such assessment instrument is the Columbia Suicide Severity Rating Scale (C-SSRS)⁶³. The C-SSRS involves a series of probing questions to inquire about possible suicidal thinking and behavior.

Only investigators who have been fully trained in the administration of the C-SSRS will assess subject suicidality. As part of training, investigators are prepared to respond to and manage instances in which patients express suicidal ideation or exhibit suicidal behavior.

At the Baseline Visit, the C-SSRS *Baseline* version will be administered. This version is used to assess suicidality over the subject's lifetime and specifically for the previous 6 month time period.

At the Week 12 and the Final Safety visit, as applicable, the *Since Last Visit* version of the C-SSRS will be administered. This version of the scale assesses suicidality since the subject's last visit.

Information obtained from: <http://www.cssrs.columbia.edu/>

8.1.9 Mobile App Study

The objective of the proposed study is to test the feasibility and utility of a novel smartphone application ('app') for monitoring disease progression in patients with Amyotrophic Lateral Sclerosis (ALS). The cell phone app will collect two broad categories of data:

- 1) "Actively collected data," wherein the subject is instructed to complete selected activities, and data about these activities is recorded, and
- 2) "Passively collected data," wherein data is recorded as the subject performs everyday activities naturally using existing cell phone sensors

Data will be collected from the subjects' smartphones over the course of the study (20 weeks), and only pre-specified forms of data will be accessed and collected by the app. In addition, the subject will be asked about their general smartphone usage.

8.1.11 Exit Questionnaire

An Exit questionnaire will be collected at Week 20 and will include a trial satisfaction survey and a blindedness questionnaire.

9 SAFETY AND ADVERSE EVENTS

The adverse event (AE) definitions and reporting procedures provided in this protocol comply with all applicable regulations and International Conference on Harmonization (ICH) guidelines. The Principal Investigator will carefully monitor each subject throughout the study for possible adverse events. All AEs will be documented on CRFs designed specifically for this purpose. It is also important to report all AEs, especially those that result in permanent discontinuation of the investigational product being studied, whether serious or non-serious.

9.1 Definitions of AEs, Suspected Adverse Drug Reactions & SAEs

9.1.1 Adverse Event and Suspected Adverse Drug Reactions

An adverse event (AE) is any unfavorable and unintended sign (including a clinically significant abnormal laboratory finding, for example), symptom, or disease temporally associated with a study, use of a drug product or device whether or not considered related to the drug product or device.

Adverse drug reactions (ADR) are all noxious and unintended responses to a medicinal product related to any dose. The phrase “responses to a medicinal product” means that a causal relationship between a medicinal product and an adverse event is at least a reasonable possibility, i.e., the relationship cannot be ruled out. Therefore, a subset of AEs can be classified as suspected ADRs, if there is a causal relationship to the medicinal product.

Examples of adverse events include: new conditions, worsening of pre-existing conditions, clinically significant abnormal physical examination signs (i.e. skin rash, peripheral edema, etc), or clinically significant abnormal test results (i.e. lab values or vital signs), with the exception of outcome measure results, which are not being recorded as adverse events in this trial (they are being collected, but analyzed separately). Stable chronic conditions (i.e., diabetes, arthritis) that are present prior to the start of the study and do not worsen during the trial are NOT considered adverse events. Chronic conditions that occur more frequently (for intermittent conditions) or with greater severity, would be considered as worsened and therefore would be recorded as adverse events.

Adverse events are generally detected in two ways:

Clinical → symptoms reported by the subject or signs detected on examination.

Ancillary Tests → abnormalities of vital signs, laboratory tests, and other diagnostic procedures (other than the outcome measures, the results of which are not being captured as AEs).

For the purposes of this study, symptoms of progression/worsening of ALS, including ‘normal’ progression, will be recorded as adverse events.

The following measures of disease progression will not be recorded as adverse events even if they worsen (they are being recorded and analyzed separately): vital capacity results and ALSFRS-R results.

If discernible at the time of completing the AE log, a specific disease or syndrome rather than individual associated signs and symptoms should be identified by the Site Investigator and recorded on the AE log. However, if an observed or reported sign, symptom, or clinically significant laboratory anomaly is not considered by the Site Investigator to be a component of a specific disease or syndrome, then it should be recorded as a separate AE on the AE log. Clinically significant laboratory abnormalities, such as those that require intervention, are those that are identified as such by the Site Investigator.

Subjects will be monitored for adverse events from the time they sign consent until completion of their participation in the study (defined as death, consent withdrawal, loss to follow up, early study termination for other reasons or following completion of the entire study).

The following will be considered Adverse Events of Special Interest regardless of severity: nephrolithiasis, urolithiasis, and gouty arthritis.

9.1.2 Serious Adverse Events

A serious adverse event (SAE) is defined as an adverse event that meets any of the following criteria:

1. Results in death.
2. Is life threatening: that is, poses an immediate risk of death as the event occurred.
 - a. This serious criterion applies if the study subject, in the view of the Site Investigator or Sponsor, is at immediate risk of death from the AE as it occurs. It does not apply if an AE hypothetically might have caused death if it were more severe.
3. Requires inpatient hospitalization or prolongation of existing hospitalization.
 - a. Hospitalization for an elective procedure (including elective PEG tube/g-tube/feeding tube placement) or a routinely scheduled treatment is not an SAE by this criterion because an elective or scheduled “procedure” or a “treatment” is not an untoward medical occurrence.

4. Results in persistent or significant disability or incapacity.
 - a. This serious criterion applies if the “disability” caused by the reported AE results in a substantial disruption of the subject’s ability to carry out normal life functions.
5. Results in congenital anomaly or birth defect in the offspring of the subject (whether the subject is male or female).
6. Necessitates medical or surgical intervention to preclude permanent impairment of a body function or permanent damage to a body structure.
7. Important medical events that may not result in death, are not life-threatening, or do not require hospitalization may also be considered SAEs when, based upon appropriate medical judgment, they may jeopardize the subject and may require medical or surgical intervention to prevent one of the outcomes listed in this definition. Examples of such medical events include blood dyscrasias or convulsions that do not result in inpatient hospitalization, or the development of drug dependency or drug abuse.

An inpatient hospital admission in the absence of a precipitating, treatment-emergent, clinical adverse event may meet criteria for "seriousness" but is not an adverse experience, and will therefore, not be considered an SAE. An example of this would include a social admission (subject admitted for other reasons than medical, e.g., lives far from the hospital, has no place to sleep).

The Site Investigator is responsible for classifying adverse events as serious or non-serious.

9.2 Assessment and Recording of Adverse Events

The Site Investigator will carefully monitor each subject throughout the study for possible AEs. All AEs will be documented on CRFs designed specifically for this purpose. All AEs will be collected and reported in the electronic data capture (EDC) system and compiled into reports for periodic reviewing by the Medical Monitor. The Medical Monitor shall promptly review all information relevant to the safety of the investigational product, including all serious adverse events (SAEs). Special attention will be paid to those that result in permanent discontinuation of the investigational product being studied, whether serious or non-serious.

9.2.1 Assessment of Adverse Events

At each visit (including telephone interviews), the subject will be asked if they have had any problems or symptoms since their last visit in order to determine the occurrence of adverse events. If the subject reports an adverse event, the Investigator will probe further to determine:

1. Type of event
2. Date of onset and resolution (duration)
3. Severity (mild, moderate, severe)
4. Seriousness (does the event meet the above definition for an SAE)

5. Causality, relation to investigational product and disease
6. Action taken regarding investigational product
7. Outcome

9.2.2 Relatedness of Adverse Event to Investigational Product

The relationship of the AE to the investigational product should be specified by the Site Investigator, using the following definitions:

1. Not Related: Concomitant illness, accident or event with no reasonable association with treatment.
2. Unlikely: The reaction has little or no temporal sequence from administration of the investigational product, and/or a more likely alternative etiology exists.
3. Possibly Related: The reaction follows a reasonably temporal sequence from administration of the investigational product and follows a known response pattern to the suspected investigational product; the reaction could have been produced by the investigational product or could have been produced by the subject's clinical state or by other modes of therapy administered to the subject. (Suspected ADR)
4. Probably Related: The reaction follows a reasonably temporal sequence from administration of investigational product; is confirmed by discontinuation of the investigational product or by re-challenge; and cannot be reasonably explained by the known characteristics of the subject's clinical state. (Suspected ADR)
5. Definitely Related: The reaction follows a reasonable temporal sequence from administration of investigational product; that follows a known or expected response pattern to the investigational product; and that is confirmed by improvement on stopping or reducing the dosage of the investigational product, and reappearance of the reaction on repeated exposure. (Suspected ADR)

9.2.3 Recording of Adverse Events

All clinical adverse events are recorded in the Adverse Event (AE) Log in the subject's study binder. The site should fill out the AE Log and enter the AE information into the Electronic Data Capture

(EDC) system within 48 hours of the site learning of a new AE or receiving an update on an existing AE.

Please Note: Serious Adverse Events (SAEs) must be reported to the Medical Monitor and Coordination Center within 24 hours of the site learning of the SAE.

Entries on the AE Log (and into the EDC) will include the following: name and severity of the event, the date of onset, the date of resolution, relationship to investigational product, action taken, and primary outcome of event.

9.3 Adverse Events and Serious Adverse Events - Reportable Events

The following are considered reportable events and must be reported to the Medical Monitor and Coordination Center within 24 hours of the site being notified of the event.

- All events that meet the above criteria for Serious Adverse Events (SAEs)
- Dosage Changes (Dose Management)
 - Investigational Product Suspension, Reduction or Re-challenge
 - Investigational Product Discontinuation
- Key Study Events:
 - Subject Final Disposition
 - Feeding Tube Placement
 - Permanent Assisted Ventilation (PAV)*
 - Tracheostomy
 - Mortality
 - Pregnancy
 - Diaphragm Pacing System (DPS) device implantation
 - Emergency or Accidental Unblinding Events

* Permanent Assisted Ventilation (PAV) is defined as more than 22 hours daily of non-invasive mechanical ventilation for more than one week (7 days). The date of onset of PAV is the first day of the seven days.

9.4 Known Adverse Event/ Experience Prophylaxis Plan

Acidic urine is a major risk factor for uric acid urolithiasis, which form from uric acid crystals. Accordingly, urine samples will be collected at in-person site visits for urinalysis to determine pH. A pre-specified algorithm will be followed for triggering urine alkalinization therapy for uric acid stone prophylaxis, starting at the Baseline visit. Because urate-elevating inosine treatment does not have an appreciable effect on urine pH as demonstrated in SURE-PD, the rate of

alkalinization due to low urine pH will be similar in placebo- and inosine-assigned subjects, mitigating any unblinding effect.

9.4.1 Alkalinization Protocol

Site staff will receive notification from the Coordination Center of the need to initiate alkalinization within a few days of the urinalysis that triggers the protocol. The following steps should then be taken:

[figure not shown]
- 1- Site staff will prescribe “lower-dose” potassium citrate, which depends on subject weight (as recorded most recently on a study visit):
 - Less than 70 kg: 10 mEq, in tablet form, po tid (with meals)
 - 70 kg or greater: 10 mEq, in tablet form, po qid (with meals and at bedtime)

- 2- Staff will phone the subject to review the purpose, administration, potential adverse effects of potassium citrate, and plan rechecking urine pH and labs (CBC and BMP) in two weeks. In addition, staff will review recommendations for adequate hydration. The prescriber should review with the subject:
 - Any contraindications to potassium citrate, including a history of peptic ulcer disease, current use of an anticholinergic agent (e.g., trihexyphenidyl), hyperkalemia or renal insufficiency per most recent electrolyte measurements, or an active urinary tract infection.
 - If potassium citrate were deemed contraindicated (or later found insufficient) then site staff may work with the Medical Safety Monitor to employ an alternative dosing schedule or an alternative alkalinizing agent such as sodium bicarbonate.
 - Potential adverse effects of potassium citrate, including minor gastrointestinal complaints, such as abdominal discomfort, vomiting, diarrhea, loose bowel movements or nausea, and rarely gastrointestinal bleeding. The subject should be instructed to check with site staff or another doctor at once if tarry stools or other evidence of gastrointestinal bleeding is noticed.
 - The possibility of abnormal results of blood lab test that will be monitored regularly on subsequent visits.
 - The importance of taking each dose faithfully, and without crushing, chewing or sucking the tablet, and to check with physician if there is trouble swallowing tablets or if the tablet seems to stick in the throat. Subjects should not change dosing alkalinization medication until instructed to do so based on follow-up urinalysis results.

- 3- Site staff will order urine pH and labs (CBC and BMP) to be collected two weeks after the initiation of urine alkalinization and will follow the algorithm in the figure to adjust

alkalinization therapy. Urine pH and labs (CBC and BMP) will be collected every two weeks as needed per algorithm illustrated in the figure.

- For subjects on “lower-dose” potassium citrate who are instructed to increase it to “higher-dose” potassium citrate, they will be instructed to double their current dose. Depending on their weight:
 - i. less than 70 kg: 20 mEq, in tablet form, po tid (with meals)
 - ii. 70 kg or greater: 20 mEq, in tablet form, po qid (with meals and at bedtime)
- 4- For any deviations from compliance with the medication site staff will contact the CCC who may engage the Medical Safety Monitor to obtain guidance.
 - 5- Subjects will be instructed to follow this algorithm for alkalinization for the duration of the treatment period of the trial. Any alkalinization therapy ongoing at the time of Week 20 visit will be discontinued immediately after that visit (or at the time of study drug discontinuation if occurring earlier) irrespective of urine pH results at the visit.

9.4.2 Lab Monitoring during Alkalinization Protocol

Current full prescribing information for potassium citrate indicates that laboratory tests should be checked every 4 months for:

- Electrolytes (to monitor for potassium elevation)
- Creatinine (to monitor for renal disease, a risk factor for hyperkalemic complications)
- CBC (to monitor for anemia as an indicator of gastrointestinal bleeding due to mucosal lesions, which have been observed rarely on solid potassium treatments – at an estimated frequency of approximately 1 lesion per 100,000 patient-years).

Under the study protocol labs will be monitored even more frequently as per algorithm above.

If hyperkalemia develops while a subject is taking potassium citrate, it should be suspended. Potassium testing should be repeated within 7 days of the suspension. If serum potassium falls back into the normal range, then the potassium citrate will be resumed at a reduced dosage in an effort to find a lower dosage that does not produce hyperkalemia but on which urine pH remains above 5. If hyperkalemia remains, the potassium citrate will be discontinued. An alternative, non-potassium-based alkalization measure may be tried if the Medical Safety Monitor and Site Investigator believe such a measure is warranted. If a non-potassium-based alkalization measure is not warranted, then the subject should discontinue study drug.

If a significant rise in serum creatinine or a significant fall in blood hematocrit or hemoglobin develops while a subject is taking potassium citrate, it should be suspended and the source of the abnormality determined. If these abnormalities are attributable to irreversible renal disease or to gastrointestinal bleeding, then the potassium citrate should not be resumed. Consideration may be given to an alternative, non-potassium-based alkalization measure if the Medical Safety Monitor and Site Investigator believe such a measure is warranted.

10 SAFETY MONITORING AND STATISTICAL ANALYSIS PLAN

10.1 Safety Monitoring

An independent Medical Safety Monitor (MSM) will review receive a quarterly report of all AEs and safety laboratory tests. Recommendations for modification or termination of the trial based on safety data will be made by the MSM to the PI and the DSMB.

The Data and Safety Monitoring Board (DSMB) will periodically review blinded, and if necessary, unblinded medical event data. SAEs, drug suspensions/rechallenges, drug discontinuations, and premature withdrawals will be tracked in real time, and the DSMB alerted if any imbalances arise between treatment groups.

Unanticipated problems involving risks to subjects or others including adverse events will be reported to the local site IRB in accordance with institutional guidelines for reporting unanticipated problems including adverse events.

If serum urate is found to be above target range (i.e. 8.1 mg/dL or higher), inosine dose will be reduced or treatment will be stopped following the pre-specified titration algorithm described in Section 6.

10.2 Statistical Considerations

10.2.1 Analysis Samples

The As-treated (AT) sample will include all subjects who receive at least one dose of study drug classified according to the actual treatment received. An intention-to-treat (ITT) sample will include all randomized subjects classified according to their randomized treatment assignment without regard to compliance with their assigned treatment. The AT sample will be used as the primary sample for analyzing safety, tolerability, efficacy, and target engagement outcomes. Secondary analyses of safety outcomes will look at the AT sample with events censored after discontinuation of inosine among participants initiated on inosine and after initiation of inosine among participants initiated on placebo should any off-label use be detected. Secondary analysis of the ITT sample will be used to estimate efficacy in preparation for future phase 3 trials.

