5.3.1 Handling of Withdrawals

A subject may choose to discontinue participation in the study at any time. However, the Site Investigator or designee will encourage subjects to continue with follow-up, regardless of their compliance with study drug. If a subject who initiated study drug permanently discontinues study drug, the SI or designee should still encourage subjects to follow the study protocol under the

modified intent-to-treat principle (ITT). These subjects will be encouraged to follow the study visits, off drug, up to the final visit. Loss to follow-up should be prevented whenever possible.

Any subject who is on study drug and needs to begin the use of any prohibited medication, must immediately discontinue use of study drug. Subjects who permanently discontinue study drug should return any unused study drug and complete early study drug discontinuation procedures per protocol.

If a subject wishes to withdraw consent, i.e., withdraw his or her participation in future study procedures, the subject will be asked to delay consent withdrawal to allow for a final safety visit and final safety telephone call. The subject will be asked to return to the study site for a final safety visit within 14 days of asking to withdraw consent. The subject will also be asked to have a final telephone call 28 days (+ 5 days) after taking their last dose of study drug.

In the event a subject no longer wishes to have their personal health information used for the analysis of this study, he or she will notify the site through an authorized letter and his or her data will no longer be included as part of the results for this study.

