10.2.2 Outcomes

10.2.2.1 Safety outcomes

The proportion of subjects experiencing one or more adverse events (AE) prior to treatment, one or more treatment-emergent (TE, defined as occurring any time after first dose of study drug) AEs, one or more severe TE AEs, one or more serious TE AEs (SAE), one or more TE AEs of special interest (AESI, including gout, gouty arthritis, and kidney stones), and one or more AEs classified by MedDRA system organ class, higher level term, and preferred term over 24 weeks in the inosine group will be compared to the placebo group using one-tailed Fisher's exact tests at $\alpha = 0.05$. The proportion of subjects experiencing one or more TE clinically significant abnormal labs for each safety assay performed or clinically significant abnormal vital signs for each vital sign monitored over 24 weeks in the inosine group will be compared to the placebo group using Fisher's exact tests. As a sensitivity analysis, we will also analyze event rates using negative binomial models for each type of event, adjusting for each participant's length of follow-up.

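### The secondary safety analysis censors subjects who stop inosine but not those who stop placebo, so its Fisher comparison is biased towards understating harm

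*Combined protocol and SAP*

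**What the plan says.** Section 10.2.1 (Analysis Samples) makes the uncensored as-treated (AT) sample primary: "The AT sample will be used as the primary sample for analyzing safety, tolerability, efficacy, and target engagement outcomes". It then adds a secondary safety analysis of the same sample with "events censored after discontinuation of inosine among participants initiated on inosine and after initiation of inosine among participants initiated on placebo", followed by the condition "should any off-label use be detected". No rule covers a subject who stops placebo.

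Section 10.2.2.1 (Safety outcomes) takes, for each event type, the proportion of subjects with at least one event over 24 weeks and compares the arms by "one-tailed Fisher's exact tests". Treatment-emergent is "defined as occurring any time after first dose of study drug". A sensitivity analysis models event rates by negative binomial regression, "adjusting for each participant's length of follow-up". The section does not tie either method to the primary or the secondary sample.

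Section 5.3.1 has subjects who permanently stop study drug stay in follow-up, whichever arm they are in: "These subjects will be encouraged to follow the study visits, off drug, up to the final visit". Section 4.3 ends treatment at Week 20 and adds a telephone interview at Week 24 that collects adverse events.

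**The concern.** Under the written rule, the same act, stopping the capsules, ends the event count in one arm only. The extra placebo time is really observed, because Section 5.3.1 keeps these subjects in follow-up. It is not event-free either: Section 9.1.1 records symptoms of ALS progression as adverse events, so events go on accruing off drug.

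A proportion with at least one event grows with the length of the window. If the inosine windows are shorter, fewer inosine subjects show an event even when the hazards are equal, and Fisher's test has no term for this. The test is one-tailed for an increase on inosine, so the shortfall works directly against finding one.

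This is the plan's only safety analysis that removes off-drug time, in a trial whose primary objective is safety and tolerability. Two gaps in the text bear on its size: whether the planned stop at Week 20 is a discontinuation, and whether a subject's follow-up length ends at the censoring date in the rate model.

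**Working it through.** **The plan's own figure.** No figure is given for the censored analysis. Section 10.2.2.5 gives the power of the comparison that it modifies: 80% for placebo proportions of 50%, 20% and 10% against 95%, 71% and 59% on inosine. Exact enumeration of a one-sided Fisher test at 0.05, with 20 inosine and 10 placebo subjects (the 2:1 ratio of Section 4.1), gives 79.7%, 80.1% and 79.7%. The figure reproduces, so these arm sizes are used below. The study workflow shows 15 and 15, which gives 82% to 84%.

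**Inputs.** From Section 10.2.2.5: placebo proportions p0 of 50%, 20% and 10%. From Sections 4.3 and 10.2.2.1: treatment to Week 20, events to Week 24. Assumed: a constant hazard, equal in the two arms unless stated; a share q of placebo subjects stopping, all at Week 8.

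**Step 1: what the asymmetry alone adds.** The hazard per week is λ = −ln(1 − p0)/24. Censoring a placebo stopper at Week 8 would give the proportion 1 − exp(−8λ). As written, that subject contributes p0. The placebo proportion is therefore raised, relative to a common rule, by q × [p0 − (1 − exp(−8λ))].

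| p0 | 1 − exp(−8λ) | Bracket | q = 5% | q = 10% | q = 25% |
|---|---|---|---|---|---|
| 50% | 20.6% | 0.294 | 1.5 points | 2.9 | 7.3 |
| 20% | 7.2% | 0.128 | 0.6 | 1.3 | 3.2 |
| 10% | 3.5% | 0.065 | 0.3 | 0.7 | 1.6 |

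The 5% column corresponds to the one early-tolerability figure in the documents: 95% tolerating treatment at 6 months in the earlier Parkinson's disease trial (Section 2.3.1).

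**Step 2: the Week 20 stop.** Suppose the planned stop counts as discontinuation of inosine and nobody stops early. The inosine proportion is then 1 − exp(−20λ) against p0 on placebo: 43.9% against 50%, 17.0% against 20%, and 8.4% against 10%, with no true difference.

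**Step 3: both together, with a real harm.** Assume p0 = 50%, 29% of each arm stopping uniformly over Weeks 0 to 20 (29% is the complement of the 71% tolerant scenario in Section 10.2.2.5), the Week 20 stop counted, and a true hazard ratio of 2.

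| Rule | Inosine | Placebo | Difference | Fisher power |
|---|---|---|---|---|
| No censoring | 75.0% | 50.0% | 25.0 points | 26% |
| As written | 60.4% | 50.0% | 10.4 | 8% |
| Same rule in both arms | 60.4% | 38.1% | 22.3 | 21% |

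With a hazard ratio of 1, the written rule gives 38.1% against 50.0%, and the common rule gives 38.1% in both arms.

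**Step 4: the rate model.** In the Step 3 setting, mean on-drug time is 0.71 × 20 + 0.29 × 10 = 17.1 weeks on inosine, against 24 weeks on placebo.

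- Follow-up truncated at censoring: events and time are cut together, and the rate ratio stays at 2.0.
- Events censored but follow-up left at 24 weeks: 2 × 17.1/24 = 1.43.
- No censoring, with the excess risk ending when inosine stops: (2 × 17.1 + 6.9)/24 = 1.71. Here censoring with truncated follow-up recovers 2.0, so it shows more harm rather than less.

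**Step 5: does a common rule cure the proportions?** Only if stopping is equally frequent. With 25% stopping inosine and 5% stopping placebo at Week 8, p0 = 50% and no true effect, it still gives 0.75 × 50 + 0.25 × 20.6 = 42.7% against 0.95 × 50 + 0.05 × 20.6 = 48.5%.

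**The case against.** The rule has a coherent rationale: censor when inosine exposure changes. A placebo subject off capsules is still unexposed to inosine. Events that lead to stopping precede it and still count. That explains the wording, but it does not make the windows comparable, and a comparison of proportions needs comparable windows.

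The rate model in Section 10.2.2.1 is not restricted to the primary sample and may well be meant for this one too. That stands. With follow-up truncated and a constant hazard ratio it is not biased in this way, but the truncation is not stated.

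The off-label condition could be read as governing the whole rule. The analysis would then run only if such use occurs. That is a further reason to rewrite the sentence.

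The size depends on assumptions. At 5% stopping placebo, Step 1 gives at most 1.5 points. The missing lag is also a lesser matter: Section 2.3.1 cites a multiple sclerosis study in which urate returned to pretrial levels within 3–5 days.

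A reader might calculate that, with 25% stopping inosine at Week 8, the inosine proportion reads 43% against 50%, so that a true hazard ratio of about 1.26 (or 1.48 with 40% stopping) would look like no difference. The arithmetic is right, but it measures the effect of censoring inosine stoppers at all. If nobody stops placebo early, a common rule gives the same 43% against 50%. It should not be cited as the size of the asymmetry.

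**Conclusion.** The point holds for the Fisher comparison in the secondary safety analysis, and it should be corrected before the analysis is run. The direction is clear: towards understating harm whenever placebo subjects stop early, or if the Week 20 stop censors inosine subjects only.

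Under a constant hazard, a 50% placebo proportion and stopping at Week 8, the asymmetry is worth 1.5 to 7.3 points for 5% to 25% stopping placebo, and less for the 20% and 10% event rates. Counting Week 20 as discontinuation costs 6.1 points (50 − 43.9) even with no early stopping.

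A reader might infer that the trial's safety conclusions in general understate harm. The documents do not support that. The primary AT analysis carries no such censoring, and a rate model with truncated follow-up is not biased this way under a constant hazard ratio.

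**What to change.** In Section 10.2.1:

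- Censor both arms at permanent discontinuation of the assigned capsules, inosine or placebo, plus one stated analysis lag common to both arms, and at any start of off-label inosine. Word it so that the off-label condition attaches only to the second trigger.
- State that the planned Week 20 stop is treated the same way in both arms.
- Truncate each subject's follow-up at the same date.

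In Section 10.2.2.1, make the negative binomial model, with the log of truncated follow-up as offset, the main analysis of this sample. Report the Fisher proportions beside it as descriptive, because windows still differ if stopping rates differ (Step 5).

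The cost is a few sentences. No new data are needed: Section 9.3 already makes discontinuation of study drug a reportable event in both arms. The small downside is slightly fewer placebo events in this secondary analysis.
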